9.9.1.1 Measurement Error(s)/Misclassification(s)

The collection of patient symptoms potentially related to adverse events of interest in the study is very limited due to the time-window since OBI application for infection to develop (27 to 72 hours after OBI application). This fact will limit the validity of these health outcomes measured after OBI application, which will need to be interpreted with caution.

9.9.1.2 **Information Bias**

Product: Peafilarastim

Self-reporting of actions and behavior intent may be biased, eg, towards a more positive effect. The development of a questionnaire carefully pre-tested before actual study start aims to minimize such a bias. Recall bias is an inherent limitation of questions asking about the past. However, the questionnaire will be administered within 72 hours post-application of Neulasta via the OBI, which will help to reduce potential recall bias.

9.9.1.3 **Selection Bias**

The study population is likely to be a convenience sample given that the approach is aimed to enhance speed of recruitment. Participation rates by potential sites/HCPs and eligible respondents may be low creating uncertainty on the level of selection bias. This is being mitigated by integrating the administration of the questionnaire into standard of care practice as much as possible. The consecutive selection of eligible respondents at

Date: 10 April 2019 Page 35 of 61

each site and the allowance of a maximum number of patients per site are also designed to minimise selection bias of respondents.

It might be discussed that the exclusion of respondents that do not read and understand the language of the questionnaire can bring a selection bias, but as the objective of the study is to evaluate the effectiveness of the PAC, the understanding of the language is needed.

The need that caregivers who will monitor the OBI administration are present at the time of application of the OBI for them to be eligible to participate as a respondent is a limitation of the study design. It cannot be discarded that this fact leads to a certain selection bias, although impact is expected to be low, as it is unlikely that caregivers not formally trained by an HCP will monitor the OBI administration.

9.9.1.4 Confounding

Product: Pegfilgrastim

A potential confounder would be the level of literacy of the respondents and/or their level of understanding of the language, which may have an impact on results. If the respondent does not understand the language (and therefore the PAC) properly, the effectiveness of the PAC will decrease, but the reason for this will be the lack of language understanding.

In order to further recognise the level of understanding of the language of the respondents, a brief health literacy questionnaire will be used to classify the patients depending on their health literacy.

9.9.2 **External Validity of Study Design**

Low participation rates by potential sites/HCPs and eligible respondents may compromise representativeness to generalise the results to the general population of persons responsible for monitoring the OBI after application.

It cannot be discarded that by participating in the study, some HCPs alter their standard practice on the distribution of the PAC. This could translate into results for study endpoints that may not be generalizable to the general population, thus impacting external validity of the study. This limitation is inherent to study design. To partially mitigate this, HCPs will be asked to follow their regular clinical practices during the conduct of the study.

Date: 10 April 2019 Page 36 of 61

9.9.3 Analysis Limitations

9.9.4 Limitations Due to Missing Data and/or Incomplete Data

Given the short time window in which the respondent needs to answer the questionnaire (27 to 72 hours after OBI application) there is an increased risk of non-response to the questionnaire, due to respondent lack of availability.

10. Protection of Human Subjects

10.1 Informed Consent

In accordance with local regulations and the ethical principles that have their origin in the principles of the Declaration of Helsinki, respondents should provide written consent before enrollment into the study. Investigators must ensure that patients or, if applicable, their caregivers, are clearly and fully informed about the purpose of the study, potential risks, the patient/caregiver's rights and responsibilities when participating in this study. If local regulations do not require an informed consent form (ICF) to be signed by the patient/caregiver, the site staff should document key elements of the informed consent process in the patient's medical record.

Informed consent for the study participation will be sought. By signing the ICF, the patient/caregiver consents to participate in the study and to be contacted by phone by the HCP for a follow up on questionnaire completion.

10.2 Institutional Review Board (IRB)/Independent Ethics Committee (IEC)

This type of study requires review and approval by a central ethics committee (EC) in the participating countries. Thus, the study will be conducted under the auspices of an independent EC (and any local EC as applicable) in each country, as defined in local regulations, and in accordance with the ethical principles that have their origin in the Declaration of Helsinki.

10.3 Patient/Caregiver Confidentiality

For the purposes of protecting the patient and the respondent's identity, a unique code will be assigned to each patient and their correspondent respondent(s), such as a series of numbers and/or letters (for example, UK-01-01-01). The data that is recorded with the patient and respondent's assigned codes is called "key-coded data". Key-coded study data will be managed by the sponsor and/or its delegates in a study-specific electronic database (the "study database"). Only the investigator and the site staff have access to the link between patient and respondent's assigned codes and the patient and respondent's identity. However, in case of an audit or inspection, subject to local laws

Protocol Number: 20170701

Date: 10 April 2019 Page 37 of 61

and regulations, government officials, IRB/EC representatives and sponsor representatives may access this information at the study site. Data that could directly identify the patient will not be collected in the "study database".

The investigator's personal data and the patient/caregiver's key-coded data, which may be included in the study database, shall be treated in compliance with all local applicable laws and regulations.

When archiving or processing personal data pertaining to the investigator and the patient/caregiver's key-coded data, all appropriate measures to safeguard and prevent access to this data by any unauthorized third party.

The investigator must retain all study records and source documents for the maximum period required by applicable regulations and guidelines, or institution procedures, or for the period specified by the sponsor, whichever is longer. The investigator must contact Amgen prior to destroying any records associated with the study.

The study documentation will be stored in the study master file.

All documentation pertaining to the study held by IQVIA will be transferred to Amgen throughout the duration of the study, and will be retained per Amgen retention policy.

Location of database and supporting documentation will be outlined in the final study report.

10.4 **Subjects Decision to Withdraw**

Product: Pegfilgrastim

Subjects have the right to withdraw from the study at any time and for any reason without prejudice to their future medical care by the physician or at the institution.

Withdrawal of consent for a study means that the subject does not wish to or is unable to continue further study participation. Subject data up to withdrawal of consent will be included in the analysis of the study, and where permitted, publicly available data can be included after withdrawal of consent. The investigator is to discuss with the subject appropriate steps for withdrawal of their consent from the study.

11. Collection, Recording and Reporting of Safety Information and **Product Complaints**

11.1 **Definition of Safety Events**

11.1.1 **Adverse Events**

An adverse event is any untoward medical occurrence in a subject/patient administered a pharmaceutical product(s) irrespective of a causal relationship with this treatment.

Protocol Number: 20170701

Date: 10 April 2019 Page 38 of 61

An adverse event can therefore be any unfavorable and unintended sign (including an abnormal laboratory finding, for example), symptom, or disease temporally associated with the use of a product(s), whether or not considered related to the product(s). The definition of an adverse event includes:

- Worsening of a pre-existing condition or underlying disease.
- Events associated with the discontinuation of the use of a product(s), (eg, appearance of new symptoms).

It is the investigator's responsibility to evaluate whether an adverse event is related to an Amgen product prior to reporting the adverse event to Amgen.

An adverse device effect is any adverse event related to the use of a medical device. Adverse device effects include adverse events resulting from insufficient or inadequate instructions for use, adverse events resulting from any malfunction of the device, or adverse events resulting from use error or from intentional misuse of the device.

11.1.2 **Serious Adverse Events**

A serious adverse event is any adverse event as defined above that meets at least one of the following serious criteria:

is fatal

Product: Peafilarastim

- is life threatening (places the patient at immediate risk of death)
- requires in-patient hospitalization or prolongation of existing hospitalization
- results in persistent or significant disability/incapacity
- is a congenital anomaly/birth defect
- is an "other significant medical hazard" that does not meet any of the above criteria

A hospitalization meeting the regulatory definition for "serious" is any in-patient hospital admission that includes a minimum of an overnight stay in a healthcare facility.

"Other significant medical hazards" refer to important medical events that may not be immediately life threatening or result in death or hospitalization, but may jeopardize the patient or may require intervention to prevent one of the other outcomes listed in the definition above. Examples of such events could include allergic bronchospasm, convulsions, and blood dyscrasias, drug-induced liver injury, events that necessitate an emergency room visit, outpatient surgery, or other events that require other urgent intervention.

Date: 10 April 2019 Page 39 of 61

11.1.3 Other Safety Findings

Other Safety Findings (regardless of association with an adverse) include:

 Medication errors, overdose, whether accidental or intentional, misuse, or abuse, involving an Amgen product,

- Pregnancy and lactation exposure,
- Transmission of infectious agents,
- Reports of uses outside the terms for authorized use of the product including offlabel use,
- Occupational exposure,
- Any lack or loss of intended effect of the product(s).

11.1.4 Product Complaints

Product Complaints include any written, electronic or oral communication that alleges deficiencies related to the identity, quality, durability, reliability, safety, effectiveness, or performance of a product or device after it is released for distribution to market or clinic by either Amgen or by distributors and partners for whom Amgen manufactures the material. This includes any drug(s) or device(s) provisioned and/or repackaged /modified by Amgen. Drug(s) or device(s) includes investigational product.

Product complaints of Neulasta and Neulasta Onpro® will be reported

11.2 Safety Collection, Recording and Submission to Amgen Requirements

This study is collecting information from patients (or their corresponding caregivers) and from HCPs at the time of Neulasta OBI application and at a point in time following Neulasta OBI administration. All safety events (adverse events, product complaints and other safety findings) considered to have occurred following subject exposure to the Neulasta OBI will be collected from Neulasta OBI application and within the following 72h with the exception of the protocol exempted events **listed below**. **IQVIA** is responsible for recording safety events that they become aware of during study period in the patient's appropriate study documentation. **IQVIA** will be responsible for reporting to Amgen any available preliminary information on a suspected safety event **that is considered serious**, within 1 business day of vendor awareness. **Non-serious Adverse events (AEs) must be reported in an expeditious manner, not to exceed 15 calendar days of** vendor awareness.

Date: 10 April 2019 Page 40 of 61

Protocol Exempted Events

Adverse events that are anticipated to occur in this study population because they are known adverse reactions to chemotherapy or are known to occur in the context of the underlying disease are not planned to be collected in this study. A list of all events and corresponding MedDRA preferred terms that are not to be collected in the study is provided in Appendix G.

If any of the exempted events have a fatal outcome, they should be considered a serious adverse event and must be collected and reported individually within 1 business day of vendor awareness unless the event is due to disease progression.

All safety information that is not specified in this section including all fatal events are to be collected and submitted to Amgen within the specified time frame.

Protocol exempted events and safety events that are suspected to be related to any medicinal product other than Neulasta OBI should be reported to the local authority in line with the local country requirements.

See Appendix C for sample Safety Report Form(s), Appendix D for Additional Safety Reporting Information regarding the adverse event grading scale used in this study, and Appendix E for sample Pregnancy and Lactation Notification Worksheets. The HCP may be asked to provide additional information for any event submitted, which may include a discharge summary or extracts from the medical record. Information provided about the event must be consistent with information recorded in the study documentation where safety data may also be recorded.

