Alkaline phosphatase	Blood alkaline phosphatase abnormal, blood alkaline phosphatase increased, blood alkaline phosphatase decreased
Bilirubin	Blood bilirubin abnormal, blood bilirubin decreased, blood bilirubin increased, blood bilirubin unconjugated abnormal, blood bilirubin unconjugated increased, blood bilirubin unconjugated decreased, blood bilirubin conjugated abnormal, blood bilirubin conjugated increased, blood bilirubin conjugated
Albumin	Blood albumin abnormal, blood albumin decreased, blood albumin decreased, hyperalbuminaemia, hypoalbuminaemia
Total protein	Hyperproteinaemia, hypoproteinaemia,

10 April 2019 Page 61 of 61

Event	MedDRA PT(s)
Magnesium	Blood magnesium abnormal, blood magnesium decreased, blood magnesium increased, protein total abnormal, protein total decreased, protein total increased
Phosphorus	Blood phosphorus abnormal, blood phosphorus decreased, blood phosphorus increased, hyperphosphataemia, hypophosphataemia
LDH	Blood lactate dehydrogenase abnormal, blood lactate dehydrogenase increased, blood lactate dehydrogenase decreased
Uric acid	Blood uric acid abnormal, blood uric acid decreased, blood uric acid increased, hyperuricaemia
CEA	Carcinoembryonic antigen abnormal, carcinoembryonic antigen increased, carcinoembryonic antigen high, carcinoembryonic antigen decreased
CA 19-9	Carbohydrate antigen 19-9 increased
CA 27-29	Carbohydrate antigen 27.29 increased
CA 15-3	Carbohydrate antigen 15-3 increased
Blood culture	Blood culture negative, blood culture positive
Urine culture	Urine culture negative, urine culture positive
Sputum culture	Sputum culture positive
Stool culture	Stool culture negative, stool culture positive
Seizures	Seizure
Epilepsy	Epilepsy
Hearing loss	Hypoacusis, deafness
Loss of vision	Visual impairment, blindness
Diplopia	Diplopia
Conjunctivitis	Conjunctivitis, adenoviral conjunctivitis, conjunctivitis bacterial, conjunctivitis viral
Excessive tearing	Lacrimation increased
Hand foot syndrome (Palmar- plantar dysesthesia)	Palmar-plantar erythrodysaesthesia syndrome
Lower/upper extremity swelling	Limbal swelling, oedema
Acid reflux	Gastrooesophageal reflux disease

Date: 10 April 2019 Page 1 of 9

Amendment 1

Protocol Title: An Observational Study to Assess the Effectiveness of the Neulasta[®] Patient Alert Card and to Measure Medication Errors Related to the Use of the Neulasta[®] On-Body Injector

Amgen Protocol Number Pegfilgrastim 20170701

Amendment Date: 10 April 2019

Rationale:

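### Section 11.2 exempts Appendix G events by preferred term with no condition on suspected relation to Neulasta or the OBI, and restores collection only for a fatal outcome

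*Protocol*

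**What the plan says.** Section 11.2 sets a general rule and then takes a list out of it. Safety events following exposure to the OBI "will be collected from Neulasta OBI application and within the following 72h with the exception of the protocol exempted events".

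The subsection on exempted events gives a reason and a mechanism. The reason is expected background: "Adverse events that are anticipated to occur in this study population because they are known adverse reactions to chemotherapy", or because they belong to the underlying disease. The mechanism is a list of terms: "A list of all events and corresponding MedDRA preferred terms that are not to be collected in the study is provided in Appendix G". Appendix G runs from alopecia and dry skin to Seizure, Epilepsy, several forms of jaundice including hepatocellular, and, under loss of vision, "Visual impairment, blindness".

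There is one route back into collection: "If any of the exempted events have a fatal outcome, they should be considered a serious adverse event and must be collected". That sentence ends by excepting events due to disease progression. The next paragraph reads "All safety information that is not specified in this section including all fatal events are to be collected and submitted to Amgen". One further sentence touches on suspected cause: "Protocol exempted events and safety events that are suspected to be related to any medicinal product other than Neulasta OBI should be reported", the destination being the local authority.

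Two definitions bear on this. Section 11.1.1 makes the investigator responsible for judging whether an adverse event is related to a product of the sponsor before reporting it. Section 11.1.2 lists the seriousness criteria and illustrates the last of them: "Examples of such events could include allergic bronchospasm, convulsions, and blood dyscrasias, drug-induced liver injury".

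**The concern.** The reason for the list and the way it operates do not match. The reason is about background: in patients on chemotherapy these events are common and say little about the injector. That is a sound ground for not collecting them when nobody suspects the product. The list, however, works on the term alone. It does not ask whether someone suspects Neulasta or the OBI in the case at hand, and a suspected reaction is exactly the case to which the background reason does not apply.

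What is at stake is the completeness of individual safety reporting to the sponsor for suspected reactions under the listed terms. Some of those terms can describe serious events. The awareness score, receipt of the PAC and the medication error proportion do not depend on it.

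**Working it through.** No figure in the plan is at issue and no formula applies. The check sets the passages side by side and follows one test case through them.

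**Size of the list.** Counting event rows over the three pages of Appendix G gives 29 + 17 + 22 = 68. The count shows the reach of the list, not the number of reactions at risk, since many rows are minor symptoms, laboratory values or tumour markers.

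**Test case.** A patient has a seizure within 72 hours of OBI application, is admitted, survives, and the HCP suspects the product.

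1. *General rule (11.2).* The event is inside the window, but the rule excepts exempted events. Seizure is an Appendix G term, so the event is out.
2. *Seriousness (11.1.2).* In-patient admission meets a seriousness criterion. The exemption text in 11.2 does not use the criteria, apart from death.
3. *Fatal outcome (11.2).* The patient survives, so this route does not apply.
4. *Relatedness (11.1.1, and the relationship column of the Appendix C form).* The judgement is asked for, but the exemption does not use the answer.
5. *Suspected cause (11.2).* The one sentence on cause concerns other medicinal products. If its qualifier is instead read as attaching only to the second item, exempted events of any cause go to the local authority. On either reading the event does not enter the study data or reach the sponsor.
6. *Residual clause (11.2).* It covers information that the section does not specify. The exempted terms are specified there, through Appendix G.

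At no step is collection of this event clearly required.

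**The four illustrations in 11.1.2 against Appendix G.**

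| 11.1.2 illustration | Appendix G |
|---|---|
| Convulsions | Direct match: Seizure (Epilepsy is also listed) |
| Drug-induced liver injury | Not listed by name; jaundice, ALT, AST, alkaline phosphatase and bilirubin terms are listed |
| Allergic bronchospasm | Not listed |
| Blood dyscrasias | Not listed |

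One of the four is exempted directly. A second is touched only through terms by which it may present.

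**Fatal events.** One sentence leaves out fatal exempted events due to disease progression. The paragraph after it asks for all fatal events. A vendor handling a death from progression under a listed term has two adjacent instructions that can be read differently.

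**Analysis.** Section 9.7.3 plans to code every adverse event that respondents report in the questionnaire and to tabulate incidence by SOC and PT. It does not mention the exemption, so it is unclear whether a listed term volunteered by a respondent is tabulated.

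**The case against.** The best answer is that the exemption carries its own limit: an event attributed to the OBI is not a background chemotherapy or disease event, so it was never exempt. That may well be what was intended. But the reason is stated for the study population, while the sentence that operates names terms that are not collected. If the narrower meaning is intended, the text should say so.

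A second answer is that other routes exist. Section 11.2 has the vendor report serious suspected safety events on becoming aware of them and does not repeat the exemption there. Section 11.2.1 has the investigator notify the ethics committee of serious adverse events. Product complaints, medication errors and lack of effect are separate categories, so an accompanying device failure could be captured without the adverse event. These points stand in part. They rule out the claim that such an event has no chance of being reported. They do not settle whether an exempted term must be collected, and the ethics committee and local authority routes do not lead to the sponsor.

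A third answer is that exemption lists are accepted practice. The ENCePP checklist in Appendix B itself foresees adverse events that are not collected. That is right, and the list as such is not criticised here.

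A reader might also infer more than the documents support:

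- *That 11.1.2 declares these events serious in themselves.* It offers them as possible examples under a conditional definition, and only convulsions match directly.
- *That the 9.7.3 tables lose their most informative cases.* The symptom examples for the questionnaire in 9.3 are fever, chills and sweating, none of them in Appendix G. Section 9.9.1.1 already asks for caution because of the short window.
- *That the two sentences on fatal events flatly contradict each other.* A specific rule followed by a residual clause is a possible reading. The wording is ambiguous rather than clearly inconsistent.

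**Conclusion.** The point holds as a gap in the wording of 11.2. As written, a non-fatal event under an Appendix G term that is suspected to be due to Neulasta or the OBI is not required to be collected or sent to the sponsor, even when it is serious. This rests on reading the list literally, by term. The stated reason points the other way but does not change what the operative sentence says.

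The size cannot be put in numbers. The protocol gives no event rates. With approximately 80 respondents, at most about 280 applications by its own estimate and a window of 72 hours each, such events are probably few. The change is still worth making, because a single suspected serious reaction can matter and the repair is small.

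The documents do not support going further and restoring every serious exempted event whatever its cause. That would bring back, for example, admissions for vomiting or diarrhoea due to chemotherapy, and would largely undo the purpose of the list. The condition that is missing is suspected relation to the study product.

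**What to change.** Add one sentence to the exempted-events text in 11.2: the Appendix G exemption does not apply to any event that the HCP or reporter suspects is related to Neulasta or the OBI; such events are collected and reported on the existing 11.2 clocks. Serious cases would then go to the sponsor within 1 business day of vendor awareness and non-serious ones within 15 calendar days. Appendix G itself can stay as it is.

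In the same amendment:

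- Reconcile the exception for fatal exempted events due to disease progression with the following paragraph on fatal events, so that a vendor has one instruction.
- State in 9.7.3 whether exempted terms reported in the questionnaire are coded and tabulated, so that a zero for such a term is not mistaken for absence of events.

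The cost is a short text change and some additional individual safety reports. Their number cannot be estimated from the protocol. The relatedness judgement is already required and the form already has a field for it, so no new data item is needed.
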